5.3 Data analysis

The following criteria will be used to determine success:

- 1. Ethical and regulatory approval for proposed methods
- 2. Proportion of outcome events identified by routine data sources that are confirmed by record review (target 100%)
- 3. Proportion of cases with no outcome event identified by routine data sources that have an event identified on record review (target 0%)
- 4. Proportion of inpatients with data collected (target 90%)
- 5. Proportion of each predictor variable recorded (target 90%)
- 6. Proportion of each risk assessment tool completed using available data (target 90%)

We will also estimate key parameters for any future implementation study:

- 1. The primary outcome event rate
- 2. Event rates for other outcomes
- 3. The proportion receiving prophylaxis in current practice
- 4. The proportion who would receive prophylaxis if alternative risk assessment tools were used

Descriptive analysis will report proportions, with a 95% confidence interval, from the 2-month pilot phase.

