3.0 Research Plan

3.1 Design

We plan to undertake two parallel streams of work over two years:

- 1. Evidence synthesis, involving systematic review, decision analysis modelling and value of information analysis;
- 2. Feasibility study, involving piloting of efficient research methods for an implementation study of VTE risk-assessment tools.

The evidence synthesis study will address the main research question and objectives 1-3. Systematic reviews will identify risk-assessment tools and use available data to estimate the accuracy of existing tools for predicting VTE in hospital inpatients. We will then develop a decision-analysis model to simulate the management of hospital inpatients according to strategies for VTE prophylaxis including prophylaxis for all, prophylaxis for none and prophylaxis according to risk-assessment tools identified in the systematic reviews. Modelling will be used to estimate the cost-effectiveness of each strategy compared to the next most effective alternative and determine the risk threshold that optimises effectiveness (QALYs) and cost-effectiveness (maximises net benefit assuming willingness to pay according to NICE thresholds). Modelling will also be used to identify key areas of uncertainty and determine the value of information required to reduce uncertainty.

The feasibility study will address objective 4. We anticipate that the design of an implementation study to evaluate the clinical effectiveness and cost-effectiveness of a risk-assessment tool in routine NHS practice will be based on the population, health technologies and outcomes outlined below, and will involve either allocation of hospitals or wards to alternative risk-assessment methods or selection of hospitals with different risk-assessment methods. The precise design and risk-assessment methods evaluated in an implementation study will depend on the results of evidence synthesis.

The primary outcome of an implementation study is likely to be the rate of symptomatic VTE. This is relatively low so a large study with an efficient design will be required to have adequate power to detect important differences in key patient groups. The feasibility study will therefore determine whether key outcomes can be reliably measured using routine data sources, such as Hospital Episodes Statistics (HES).

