3.6 Outcomes

DVT: a filling defect identified by ultrasound or venography or CT scan, or a positive image on MR direct thrombus imaging, within the inferior vena cava, common iliac, internal iliac, external iliac, common femoral, superficial femoral, popliteal trifurcation, posterior tibial, peroneal, gastrocnemius or soleal veins of the leg.

Clinically detected DVT: a DVT with symptoms of leg pain, swelling or discolouration that is identified during routine patient care.

Screening-detected DVT: a DVT, with or without symptoms, that is not identified during routine patient care but is detected if radiological screening is undertaken.

PE: a filling defect reported to be pulmonary embolism found on CT pulmonary angiography or digital subtraction angiography in a branch of the pulmonary artery. Or else a high probability perfusion or ventilation-perfusion scan.

Major bleeding: as defined by the International Society of Thrombosis and Haemostasis (Schulman 2005).

Clinically relevant non-major bleeding: as defined by International Society of Thrombosis and Haemostasis (Schulman 2005).

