5.0 Work stream 2: Feasibility study

The feasibility study will pilot efficient research methods for an implementation study of VTE risk-assessment tools and estimate key parameters for study design. The implementation study design will be determined by the findings of the evidence synthesis but is likely to involve either a cluster design in which wards or hospitals are allocated to alternative risk-assessment strategies or an observational design in which hospitals using different strategies are compared. The study population, setting, health technologies being assessed and outcomes are likely to be those defined above, with the primary outcome being any clinically-relevant VTE. The feasibility of such a study will depend upon our ability to undertake efficient intervention and outcome data collection from a large study population.

The feasibility study will involve an iterative process of developing and testing data collection methods but ultimately aims to determine the feasibility of (1) using routine administrative data to measure VTE and bleeding outcomes, and (2) collecting standardised VTE risk assessment data as part of routine practice. The feasibility study will be an observational study. We will not attempt to change practice or implement any risk-assessment methods. The target population, health technology and outcomes of interest are as defined in the overview of the research plan above.

Objective 1 will be addressed by determining whether routine administrative data sources correctly code VTE or bleeding events, verified by review of hospital records. The reference standard for this assessment will be based on expert review of identified cases, using the outcome definitions provided above.

Objective 2 will be addressed by determining the proportion of cases in which each key risk predictor is routinely recorded in a standardised risk assessment. The key risk predictors will be selected and defined by an expert panel drawing upon items used in existing risk-

assessment tools and their expert clinical knowledge. The PPI members of the research team will work with representative groups to review the acceptability of using each risk predictor to determine whether prophylaxis is given.

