To determine the validity of efficient methods for identifying outcomes we will undertake case note review of all events identified through routine data sources and a sample of cases with no event identified. Research nurses will review hospital records and record details of any outcome events up to 90 days and enter the data on to a standardised Case Report Form (CRF). Two independent experts will then review anonymised data collected on the outcome events and determine whether they are classified as outcomes according to definitions determined by an independent adjudication panel. Discordant judgements will be resolved through discussion and, if appropriate, independent assessment by a third reviewer.

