5.4 Sample size

The sample size is only estimated for the 2-month pilot phase in which we test the data collection methods. The initial iterative developmental phase will collect data in each cycle until a reasonably reliable conclusion can be drawn regarding the issue of interest. The broad inclusion criteria and lack of requirement for consent means that there are few practical limitations to patient numbers.

We plan to identify 3000 inpatients over 2 months across 4 hospitals. This will allow key parameters to be estimated with a high degree of precision across the whole cohort (standard error <1%) and an acceptable degree of precision in specific patient groups.

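### Success criteria 2 and 3 do not measure what share of true events routine coding captures, and their 100% and 0% targets cannot grade coding quality

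*Protocol*

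**What the plan says.** The purpose is set out twice. Section 3.1 says the feasibility study will "determine whether key outcomes can be reliably measured using routine data sources". Section 5.0 says its first objective will be met by "determining whether routine administrative data sources correctly code VTE or bleeding events, verified by review of hospital records".

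The verification design is in section 5.2: "case note review of all events identified through routine data sources and a sample of cases with no event identified". The number of non-event notes is not given there.

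The decision measures are in section 5.3, introduced by "The following criteria will be used to determine success". Two of the six concern outcome coding:

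- Criterion 2: "Proportion of outcome events identified by routine data sources that are confirmed by record review (target 100" per cent).
- Criterion 3: "Proportion of cases with no outcome event identified by routine data sources that have an event identified on record review (target 0" per cent).

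Section 16.2 refers back to this list as the criteria for feasibility. Section 5.3 adds that proportions will be reported with 95% confidence intervals. It gives no tolerance or minimum acceptable value for either criterion, and it does not list sensitivity.

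**The concern.** Criterion 2 is a positive predictive value (PPV). Criterion 3 is 1 minus a negative predictive value (NPV), because its denominator is patients with no coded event. When the outcome is rare, nearly all of those patients are true negatives, so the proportion is small however poor the coding.

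A later implementation study that takes its primary outcome from routine data needs to know what share of true events those data capture. That is sensitivity, and no criterion asks for it. Low sensitivity would under-count the later study's primary outcome, and criterion 3 would show this only as a fraction of a percentage point. A target of exactly 100% or 0% also leaves no means of grading a result that falls a little short.

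**Working it through.** **Inputs**

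- Cohort: "We plan to identify 3000 inpatients over 2 months across 4 hospitals" (section 5.4).
- Event rate p: not stated. Section 3.1 says only that symptomatic VTE is fairly uncommon. Assumed here: 0.5%, 1%, 2% and 5%. The 1.0% in the literature section is a treatment threshold from a cited US decision model, not a rate for this cohort.
- Non-event notes reviewed, m: not stated. Range shown: 100 to 500.
- Coded events, k: not stated. Shown: 15 and 30. At a 1% rate, 0.01 × 3000 = 30 events; half of them coded is 15.
- Specificity is taken as 1 in the illustrations.

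**1. The plan's own precision figure.** Section 5.4 states a standard error below 1%. The worst case is √(0.5 × 0.5 / 3000) = 0.91%, so the figure is right for a whole-cohort proportion. It does not carry over to criterion 2, which rests on the coded events alone, or to criterion 3 if only a sample is reviewed.

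**2. What criterion 3 measures.** With sensitivity Se and specificity Sp,

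criterion 3 = p(1 − Se) / [p(1 − Se) + (1 − p)Sp].

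This stays at or below p whenever Se + Sp ≥ 1. With Sp = 1 it becomes p(1 − Se)/(1 − p·Se). If every event were missed (Se = 0), it would equal p. At p = 1% and Se = 50%, it is 0.005/0.995 = 0.50%.

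| Assumed event rate | Half of events missed | 90% captured |
|---|---|---|
| 0.5% | 0.25% | 0.05% |
| 1% | 0.50% | 0.10% |
| 2% | 1.0% | 0.20% |
| 5% | 2.6% | 0.52% |

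At a 1% rate, good and poor capture differ by 0.4 percentage points.

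**3. Criterion 3 read strictly (target met only if no missed event is found).** The chance of finding none in m reviews is (1 − c)^m, where c is the true value of criterion 3. At a 1% rate:

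| Notes reviewed | Half missed (c = 0.503%) | 90% captured (c = 0.101%) |
|---|---|---|
| 100 | 60% | 90% |
| 200 | 37% | 82% |
| 300 | 22% | 74% |
| 500 | 8% | 60% |

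Poor coding therefore passes more often than not with 100 reviews, and good coding misses the target about 40% of the time with 500. Sampling without replacement from the finite cohort lowers these chances slightly. For example, 3 missed events among 2973 non-coded patients and 500 reviews give about (1 − 500/2973)³ = 58% rather than 60%.

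A clean 0/300 has an exact 95% upper limit of 1.22%. Applied to 2985 non-coded patients, that is about 36 missed events. With 15 confirmed coded events it is compatible with a sensitivity as low as 15/(15 + 36.4) = 29%.

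**4. Criterion 2.** The chance that all k coded events are confirmed is PPV^k. At a true PPV of 95%, 0.95^15 = 46% and 0.95^30 = 21%. At 99%, 0.99^30 = 74%. One unconfirmed case gives 14/15 = 93.3% or 29/30 = 96.7%, and the target is missed. In the other direction, 15/15 has an exact 95% lower limit of only 78%.

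**5. Sensitivity instead.** If every note were reviewed and there were 30 events, 15/30 = 50% (exact 95% interval 31% to 69%) and 27/30 = 90% (73% to 98%) do not overlap. With a sample, each missed event found counts for (non-coded patients)/(notes reviewed). With 15 confirmed coded events and 300 of 2985 non-event notes reviewed, the weight is 2985/300 = 9.95. One missed event found gives 15/(15 + 9.95) = 60%; two give 15/(15 + 19.9) = 43%. The measure is on the right scale, but a single finding moves it a long way.

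**The case against.** **Target may mean aspiration.** The protocol uses the same word for its 90% items, does not say how the six criteria combine, and plans estimates with intervals. Nothing says that 29 of 30 confirmed would stop the programme. That is fair, and the PPV estimate would remain informative. But the list is stated to decide success, and if the targets are only aspirations, no rule separates success from failure.

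**Sensitivity can be recovered.** All coded events and a sample of non-events are reviewed, so a known sampling fraction is enough. The sample size, weighting and interval method may also sit in an analysis plan that is not at hand, and their absence is not counted here. This stands. The point is confined to the choice of decision measure and targets, which the protocol does fix.

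**The event rate is assumed.** It is, and bleeding counts as well as VTE, so the combined rate may be higher and criterion 3 less close to zero. The bound holds at any rate.

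**Stronger readings that the documents do not support.**

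- A reader might infer that the study would probably report criterion 3 as met while half of VTE is missed. At a 1% rate, (1 − 0.00503)^m exceeds one half only up to about 137 reviews, and the protocol gives neither number.
- A reader might infer that the verdict would be wrong in both directions. That requires reading criterion 2 strictly and criterion 3 loosely. Read strictly, one missed event fails criterion 3 too.
- A reader might infer that disagreement is built in, because section 5.2 speaks of any coded VTE while the DVT definition in section 3.6 ends its list of sites with "popliteal trifurcation, posterior tibial, peroneal, gastrocnemius or soleal veins of the leg". The wording in 5.2 describes a future study's outcome, no code list is given, and 5.2 also refers to definitions set by an adjudication panel. Discordance is not shown.

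**Conclusion.** The point holds as a fault in the stated decision criteria. Criterion 3 is bounded by the event rate whenever coding is better than chance, which follows from algebra alone. Its size in practice rests on the assumed rates: from 0.5% to 5%, missing half of all events moves it only to between 0.25% and 2.6%. Against a strict 0% target, the result is driven mainly by the number of notes reviewed; against a loose one, good and poor capture both look close to zero. Criterion 2 is a sensible measure with a target that one unconfirmed case defeats. The share of true events captured, which the objectives in sections 3.1 and 5.0 need, is not a criterion.

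The documents do not support a forecast of which way the feasibility decision would go. The event rate, the number of coded events and the number of non-event reviews are all unstated.

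**What to change.** In section 5.3:

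1. Replace criterion 3 with the sensitivity of routine coding: confirmed coded events divided by all confirmed events. Weight missed events found in the non-event sample by the inverse of the sampling fraction. Report VTE and bleeding separately, with exact or weighted 95% intervals as the sampling requires.
2. Keep PPV as criterion 2.
3. Replace the 100% and 0% targets with minimum acceptable values for PPV and sensitivity, agreed before data are seen, and say whether the estimate or a confidence limit must reach them.

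The measures can be computed from the reviews already planned. The cost is a weighted analysis and a sensitivity interval that may be wide if few non-event notes are reviewed. Enriching the non-event sample with patients flagged in hospital systems (for example by VTE imaging or readmission) could find more missed events for a given number of reviews. That is optional and may add work at the four hospitals.

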5.4 Sample size

The sample size is only estimated for the 2-month pilot phase in which we test the data collection methods. The initial iterative developmental phase will collect data in each cycle until a reasonably reliable conclusion can be drawn regarding the issue of interest. The broad inclusion criteria and lack of requirement for consent means that there are few practical limitations to patient numbers.

We plan to identify 3000 inpatients over 2 months across 4 hospitals. This will allow key parameters to be estimated with a high degree of precision across the whole cohort (standard error <1%) and an acceptable degree of precision in specific patient groups.

6.0 Trial Supervision

The University of Sheffield will act as Sponsor for the trial. A Study Steering Committee (SSC) and a Project Management Group (PMG) will be established to govern the conduct of the study. These committees will function in accordance with Sheffield CTRU standard operating procedures.

6.2 Study Steering Committee

A Study Steering Committee will provide independent oversight to the study. This will consist of an independent chair, independent experts in VTE, orthopaedics and internal medicine, independent PPI representatives, along with SG and DHo from the study team. Independent members will be recommended to the HTA programme by the lead applicant. The SSC will primarily be responsible for providing independent oversight of the feasibility study but will also provide advice and expert input, as required, to the evidence synthesis. The SSC will meet at regular intervals as outlined in the SSC terms of reference. The SSC can prematurely close the trial following advice from the sponsor, funder or PMG.

7.0 Data handling and record keeping

Participant confidentiality will be respected at all times and no patient identifiable data will be accessed by anyone outside of the clinical care team.

The clinical research nurses will be provided with a password-protected database that will be used to store data on an NHS computer. Only they will have access to this database. They will periodically send anonymised data to the University of Sheffield Clinical Trials Research Unit via a secure electronic transfer.

7.1 Archiving

Study records will be stored for a period of 10 years after the completion of the trial before being destroyed.

8.0 Dissemination, outputs and anticipated impact

The main outputs of the study will be:

- 1. An optimal strategy for providing prophylaxis, based on current evidence
- 2. Risk thresholds that optimise effectiveness (QALYs) and cost-effectiveness
- 3. Value of information for future research
- 4. A proposal for a feasible implementation study

Outputs 1 and 2 will inform policy and practice. We will submit open-access scientific papers reporting these outputs to high impact general medical journals to ensure the widest possible awareness, accessibility and impact. We will present our findings at relevant scientific meetings, especially those attended by clinicians working in haematology, general medicine and orthopaedics. We will send professionals summaries of our findings to relevant professional organisations. We also send professional summaries to VTE leads at acute hospitals.

This study is intended to inform future NICE guidance for reducing the risk of hospitalacquired VTE. We will therefore make contact with the NICE Guideline Development Group and provide professional summaries, published papers and the full HTA report.

We will disseminate plain language summaries of our findings to the public and patients through our collaborating PPI groups (SECF and Thrombosis UK). We will also offer to present our findings at any professional or public meetings organised by SECF or Thrombosis UK.

Outputs 3 and 4 will inform future research priorities. We will provide research recommendations based on our findings that will be fed back to the commissioning arm of the HTA programme to determine what (if any) future research should be commissioned. We will also disseminate professional and plain language summaries, along with the full report, to relevant professional, public and patient representative organisations so they are able to make a fully informed contribution to any future research prioritisation process. Our full findings will be published in the open-access NIHR report. We will use submissions to scientific journals, online academic forums and social media to ensure that the research community is aware of our findings, so that any interested research groups are in a position to draw upon our findings in developing future research proposals.

9.0 Project timetable

The project will take place over 2 years, according to the GANTT chart below. We will provide progress reports covering the following elements of the study at the end of each of six-month phase:

- 1. Systematic review update; confirmation of set-up and regulatory submissions for the feasibility study
- 2. Decision-analysis modelling and value of information analysis; pre-piloting for the feasibility study

3. Write-up and dissemination of the evidence synthesis; data collection piloting in the feasibility study

	Q1	Q2	Q3	Q4	Q5	Q6	Q7	Q8
EVIDENCE SYNTHESIS								
Systematic review								
Decision analysis modelling								
Writing up and dissemination								
FEASIBILITY STUDY								
Ethics & Confidentiality Advisory Group approvals								
Piloting data collection								
Piloting record linkage								
Analysis and write-up								

10.0 Funding and role of the funder

This study has been funded by the National Institute for Health Research (NIHR) Health Technology Assessment programme. The funder has reviewed the research protocol but will have no role in data collection, analysis, data interpretation, report writing or in the decision to submit the report for publication.

11.0 Ethics

The evidence synthesis work stream will only use secondary research methods, carries no significant ethical risk and therefore does not require ethical approval. The feasibility study work stream only involves observational methods, with no change to patient care, so ethical risks are low and mainly related to patient confidentiality and data protection.

The main ethical issue relates to using patient data without consent. This is justified, both ethically and with regard to General Data Protection Regulations, on the basis of medical research in the public interest. An implementation study requires a large, unselected patient population that includes all people at risk of VTE. It would therefore not be feasible to seek patient consent to use their data and the ethical risks of causing distress and confusion by seeking consent for secondary data use would outweigh the ethical benefits. We will only use anonymised data in the analysis and will put in place a process to minimise the risks to patient confidentiality.

As outlined in the data collection section, we will explore using standardised, routinelyrecorded risk-assessment information. This is collected by the clinical team as part of routine care and will be extracted by research nurses in the participating hospitals. Only anonymised details will be used by the research team. However, we will need to link risk-assessment data to outcomes recorded in routine clinical coding used to generate Hospital Episodes Statistics and then review hospital records to determine the accuracy of the clinical coding. We will explore whether this can be feasibly done within the hospital or whether personal data need to be used to link with data collected nationally by NHS Digital.

In the first six months of the project we will secure Research Ethics Committee approval and HRA approval to undertake the feasibility study. Initially this will be on the basis of only members of the clinical care team (including research nurses) using personal data. If this does not allow data linkage to support an efficient study, we will seek CAG section 251 approval to use personal data to link hospital data with NHS Digital data.

